7.5. Analysis Methods

Frequencies and percentages will be presented at the time points specified above for the specified parameters. The denominator is the number of subjects with sequencing data at the selected time point.

A frequency output and/or figure will only be generated if number of participants with respective sequence information available (i.e. baseline sequence info for baseline outputs and paired baseline/post-baseline sequence info for post-baseline outputs) for that respective output or figure is greater or equal to 5 ($N \geq 5$).

For comparison of amino acid or nucleotide levels to universal or genotype specific HBV reference sequences descriptive summaries may be performed by subgroups.

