
 To explore the impact of study intervention on participants' self-stigma and health-related quality of life using patient-reported outcomes (PROs) during study intervention and follow-up and to assess the psychometric properties of the HBV-specific self-stigma scale. 	
 Changes over time in score on the HBV-specific self-stigma scale. Psychometric properties of the HBV-specific self-stigma scale. Changes over time in the 5-Level EuroQol 5-Dimension (EQ-5D-5L) Visual Analog Scale (VAS) score and Index score.

 To explore the relationship of PK with selected pharmacodynamic (PD) parameters of efficacy 	
 Relationship of various PK parameters with selected efficacy and safety

Objectives	Endpoints
and safety.	endpoints.

 To explore the HBV genome sequence during study intervention and follow-up. 	
 Assessment of intervention-associated mutations.

 To explore HBV-specific T-cell responses during study intervention and follow-up.* 	
 Changes from baseline in HBV-specific peripheral blood T-cell responses.

* Peripheral blood mononuclear cell (PBMC) samples for immune analyses will be collected at selected sites only.

Refer to Section 8, Study Assessments and Procedures for evaluations related to endpoints.

For the definitions of terms, refer to Section 10.1, Appendix 1, Abbreviations and Definitions of Terms.

HYPOTHESIS

The primary hypothesis of this study is that the combination regimen of JNJ-3989+JNJ-6379+NA is more efficacious than NA treatment alone, as measured by the primary efficacy endpoint, the proportion of participants with HBsAg seroclearance at Week 72 (ie, 24 weeks after completion of all study interventions at Week 48) without restarting NA treatment.

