7. VIRAL GENOME SEQUENCE ANALYSIS

The sequencing of samples from participants in this study may be triggered by the sponsor virologist based on changes in HBV DNA levels observed in each individual subject and the limits of the sequencing assay.

Viral genome sequence analysis will be performed to evaluate the presence of genetic variations (including substitutions) associated with JNJ-56136379, JNJ-3989, and/or ETV or TDF/TAF treatment on both nucleotide and/or amino acid level.

Sequencing of the HBV genome will be performed to monitor HBV variants present at the time points indicated in Section 7.1.

Virology results will be presented by specified timepoints and genetic region and position of interest. A separate virology report will be prepared.

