7.1. Time Points and Samples

When analyzing sequencing data, the focus will be on genetic variants at

- Time Point of Sequence at Virologic Breakthrough: time point with sequence data available closest to the time point of virologic breakthrough (FTPT) (see Section 5.3.1.1.7 for virologic breakthrough definition)
- Time Point of Sequence at Virologic Flare: time point with sequence data available closest to the time point of Virologic flare (see Section 5.3.1.1.6 for virologic flare definition)
- Time Point of Sequence at Re-treatment during Post-treatment Follow-up: time point with sequence data available closest to time point where re-treatment criteria is met (see Section 5.3.1.1.8)
- Aggregated Post-Baseline Study Period (ASSEQ): entire post-baseline study period, aggregate of all available time points in the study with sequence data available
- Aggregated Post-Baseline Treatment Period (ATSEQ): entire post-baseline treatment period, aggregate of all available post-baseline time points during the treatment phase with sequence data available

Given only participants who are on stable NA treatment and who have HBV DNA <60 IU/mL at screening will be enrolled in this study, no baseline sequencing can be performed. In the exceptional case baseline HBV DNA levels are above the sensitivity limit of the sequencing assay used, the baseline sample may be sequenced.

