7.3. Parameters to Analyze

At specified time points and for each list specified in the section below, the following parameters will be analyzed:

- Number (%) of subjects with a substitution at a specific position.
- Number (%) of subjects with a specific substitution.
- Number (%) of subjects with a specific substitution profile
- Number (%) of subjects with substitutions on amino acid level (overall and by HBV genotype (A, B, C, D, E, F, G, H, I and Unknown))
 - in the HBV core protein,
 - at HBV core protein positions of interest,
 - at positions of interest in the RT-domain of the polymerase,
 - at positions of interest in the major hydrophilic loop of HBsAg.
- Number (%) of subjects with substitutions on nucleotide level
 - at the binding site positions of JNJ-3989 (i.e. JNJ-3976 and JNJ-3924) (overall and by HBV genotype (A, B, C, D, E, F, G, H, I and Unknown)).
 - in the precore (genome position 1896) and basal core promotor (genome positions 1762/1764) region (overall, by HBV genotype (A, B, C, D, E, F, G, H, I and Unknown))

The focus will be on substitutions at a time point, and reversion to wild type state. The above summaries will be repeated for genetic variations (not needed for CSR).

In the sequence analysis, sequences will be mapped to the respective genotype specific reference sequences after which nt changes and aa substitutions will be annotated compared to the respective genotype specific reference (see Table in Section 7.2). In addition, the X02763 (HBV genotype

A), which is the master reference sequence of the HBV db, will be used as universal reference sequence.

All NGS data will be collected using a nt and aa read frequency cut-off of ≥ 0.01 . For the analysis of nt changes and/or aa substitutions in terms of frequency of variant, a read frequency cut-off of ≥ 0.15 will be used. The persistence of nt changes and aa substitutions will be evaluated using a cut-off of ≥ 0.15 and ≥ 0.01 .

The applicability of the sequencing approach described here (eg, the 0.01 sensitivity limit) will be assessed during the development program and might be adapted if needed.

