7.5.1. Post-Baseline

- Time of Virologic Breakthrough (if applicable)

For virologically suppressed participants who experience virologic breakthrough but who don't have baseline sequence information available, the frequency of genetic variations (with a primary focus on substitutions) at time of viral breakthrough will be tabulated in frequency outputs (n, %), based on NGS data (1% and 15% cut-off), for participants with viral sequence info available at time of viral breakthrough.

The return to wild type for subjects with virologic breakthrough and genetic variations at time of virologic breakthrough will be tabulated in frequency outputs based on NGS data, as well as the genetic variations in subjects who did not return to wild type.

- Time of Virologic /Clinical Flare (if applicable)

For virologically suppressed participants who experience virologic/clinical flare but who don't have baseline sequence information available, the frequency of genetic variations (with a primary focus on substitutions) at time of virological/clinical flare will be tabulated in frequency outputs (n, %), based on NGS data (1% and 15% cut-off), for participants with viral sequence information available at time of flare.

The return to wild type for subjects with virologic/clinical flare and genetic variations at time of virologic/clinical flare will be tabulated in frequency outputs based on NGS data, as well as the genetic variations in subjects who did not return to wild type.

- Time of Re-treatment during Post-treatment Follow-up

For virologically suppressed participants who meet NA re-treatment criteria but who don't have baseline sequence information available, the frequency of genetic variations (with a primary focus on substitutions) at time of meeting NA re-treatment criteria will be tabulated in frequency outputs (n, %), based on NGS data (1% and 15% cut-off), for participants with viral sequencing information available at time of meeting NA re-treatment criteria.

The return to wild type for subjects who meet re-treatment criteria during follow-up and genetic variations at time of meeting the re-treatment criteria will be tabulated in frequency outputs based on NGS data, as well as the genetic variations in subjects who did not return to wild type.

- Other Post-Baseline

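### SAP 7.5 makes post-baseline sequence tables depend on at least 5 paired baseline sequences, which SAP 7.1 says will almost never exist, and SAP Section 7 does not ask for those tables by arm

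*SAP*

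**What the plan says.** The exploratory endpoint in Protocol Section 3, repeated in SAP 1.1, is "Assessment of intervention-associated mutations". The relevant SAP rules are these.

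- **Baseline sequences (SAP 7.1).** Because participants are suppressed on NA and have HBV DNA below 60 IU/mL at screening, "no baseline sequencing can be performed". There is one exception: "In the exceptional case baseline HBV DNA levels are above the sensitivity limit of the sequencing assay used, the baseline sample may be sequenced".
- **Definition of a variation (SAP 7.2).** A variation is a difference from a genotype-specific or universal reference sequence, not from the participant's own baseline.
- **Output rule (SAP 7.5).** A post-baseline frequency output or figure is generated only if the number of participants with "paired baseline/post-baseline sequence info for post-baseline outputs) for that respective output or figure is greater or equal to 5".
- **Denominator (SAP 7.5, just before the output rule).** "The denominator is the number of subjects with sequencing data at the selected time point".
- **Planned tables (SAP 7.5.1).** For participants with breakthrough who lack "baseline sequence information available, the frequency of genetic variations (with a primary focus on substitutions) at time of viral breakthrough will be tabulated". Parallel text covers virologic or clinical flare and meeting the NA re-treatment criteria.
- **Breakdowns (SAP 7 and 7.3).** "Virology results will be presented by specified timepoints and genetic region and position of interest", and the counts include "Number (%) of subjects with substitutions on amino acid level (overall and by HBV genotype". SAP 7.5 allows optional summaries by unnamed subgroups. Intervention arm is not named anywhere in Section 7.

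**The concern.** There are two linked problems.

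First, the output rule asks for something that the same section says will not normally exist. A programmer cannot satisfy both SAP 7.5 and SAP 7.5.1: either the threshold is ignored or the planned tables are not produced.

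Second, when variation is measured against a reference sequence and a baseline is missing, a polymorphism carried before treatment counts the same as a variant selected during treatment. The NA-alone participants stop treatment at the same time. Protocol 2.1 expects HBV DNA to rebound in most patients after NA is stopped, and the follow-up Schedule of Activities collects sequencing samples, so this arm should yield some sequences. It is therefore the main internal guide to background variation, and pooled tables would hide it.

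At stake is the readability of the resistance tables for JNJ-6379 and JNJ-3989. This matters because Protocol 2.2.1 reports that all 5 participants with breakthrough on 75 mg JNJ-6379 monotherapy had an emerging T33N core mutation.

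**Working it through.** The plan gives no calculated figure on this point. Its only number is the threshold of 5, so the check is mainly a reading of the rules against each other, with a small calculation for scale.

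**Step 1: count pairs in the tables that SAP 7.5.1 plans.** The breakthrough, flare and re-treatment tables are defined on participants without a baseline sequence. Such a participant cannot contribute a baseline/post-baseline pair. Pairs = 0, required = 5, so each table fails the rule however many post-baseline sequences are available.

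**Step 2: a more generous reading.** Suppose the rule counts everyone sequenced at the time point, including the exceptional participants with a baseline sequence. Let n be the number with a post-baseline sequence and q the share of them with a usable baseline sequence. Then

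P(at least 5 pairs) = 1 − Σ(k=0..4) C(n,k) q^k (1−q)^(n−k).

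The documents give neither n by event nor q; both are assumed here. The value n = 120 is the whole target sample and so the upper limit.

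| Assumed q | n = 20 | n = 60 | n = 120 |
|---|---|---|---|
| 0 | 0 | 0 | 0 |
| 1% | <0.0001 | 0.0003 | 0.0074 |
| 2% | <0.0001 | 0.0070 | 0.0938 |
| 5% | 0.0026 | 0.1803 | 0.7218 |
| 10% | 0.0432 | 0.7290 | 0.9944 |

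For example, n = 20 and q = 5% gives 1 − (0.3585 + 0.3774 + 0.1887 + 0.0596 + 0.0133), or about 0.0026. The rule is likely to be met only if many participants are sequenced and baseline sequences are fairly common, which is not what SAP 7.1 describes.

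**Step 3: compare the rule with its own denominator.** Percentages in SAP 7.5 are taken over participants with sequence data at the time point, with no pairing. A threshold on that same count would be consistent; a threshold on pairs is not.

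**Step 4: what pooling hides.** If sequenced participants split 2:1 as randomised (an assumption), pooled frequency = (2 × active + control)/3. A pooled 30% then fits three different pictures:

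- active 30%, control 30%: (60 + 30)/3 = 30%
- active 40%, control 10%: (80 + 10)/3 = 30%
- active 20%, control 50%: (40 + 50)/3 = 30%

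**Step 5: is arm required elsewhere?** Protocol 9.4.1 calls for all efficacy summaries by arm, and Resistance Analyses is its subsection 9.4.1.3, although that subsection does not mention arm. SAP 5 analyses all efficacy data by arm. In the SAP, however, sequencing sits in a separate Section 7. The sections on adverse events (6.1.2), immune response (8.3) and self-stigma (9.1.2) each name arm; Section 7 does not.

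**The case against.** The best defence is that the specific text should prevail over the general. SAP 7.5.1 sets out tables for participants without a baseline sequence, and a parenthesis that would void them looks like a carry-over slip. That is probably the intent, but it concedes the contradiction, and the SAP does not say which text governs.

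A reader might go further and infer that intervention-associated mutations cannot be assessed at all. The documents do not support that:

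- The rule covers frequency outputs and figures only. SAP 7.5.1 and 7.5.2 list variations for all subjects, and SAP 7 announces a separate virology report.
- SAP 7.3 plans counts by specific position, substitution and profile. A substitution already known to matter, such as T33N, can be recognised without a baseline.
- Return to wild type and persistence give some within-participant information.

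A reader might also infer that the plan never presents these data by arm. That is true of SAP Section 7 taken alone, but Protocol 9.4.1 and SAP 5 set the general rule. The gap is that Section 7 does not carry it over.

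Finally, it is tempting to call a variant intervention-associated only when its frequency exceeds that in the NA-alone arm. That should not be adopted. Sequenced participants are selected after randomisation, by rebound and by the sponsor virologist's decision to sequence, so the contrast is not a randomised one. With few participants per cell, such a rule could also dismiss a recognised resistance substitution.

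**Conclusion.** The output rule is wrong as written. It conflicts with SAP 7.1, with the denominator in SAP 7.5 and with the tables in SAP 7.5.1. Followed literally, it removes the three event tables outright. It would also remove most or all other post-baseline frequency tables if baseline sequences are as exceptional as SAP 7.1 says; that second part depends on the assumed q and n above. Separately, SAP Section 7 omits the by-arm presentation that the protocol's general rule implies. Without it, pooled frequencies are hard to interpret, because variation is defined against a reference and almost no baselines exist.

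The reach is limited. This is one exploratory endpoint, reported descriptively, and the listings survive. No primary, secondary or safety conclusion changes.

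**What to change.** 1. **SAP 7.5.** Generate a post-baseline frequency output or figure when at least 5 participants have sequence data at that time point. Keep the paired condition only for outputs that show change from baseline.
2. **SAP 7.3 and 7.5.1.** Present the frequency tables and listings by randomised arm, then by HBV genotype, with no formal test. Add a note that sequenced participants are a post-randomisation selection and that per-arm cells may be small.
3. **Interpretation.** Use the NA-alone frequencies as a descriptive guide to background variation, without making excess over control a condition for reporting a variant as intervention-associated.

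The cost is a few lines of SAP text and an arm column in tables already planned. No new samples or assays are needed.

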7.5.1. Post-Baseline

- Time of Virologic Breakthrough (if applicable)

For virologically suppressed participants who experience virologic breakthrough but who don't have baseline sequence information available, the frequency of genetic variations (with a primary focus on substitutions) at time of viral breakthrough will be tabulated in frequency outputs (n, %), based on NGS data (1% and 15% cut-off), for participants with viral sequence info available at time of viral breakthrough.

The return to wild type for subjects with virologic breakthrough and genetic variations at time of virologic breakthrough will be tabulated in frequency outputs based on NGS data, as well as the genetic variations in subjects who did not return to wild type.

- Time of Virologic /Clinical Flare (if applicable)

For virologically suppressed participants who experience virologic/clinical flare but who don't have baseline sequence information available, the frequency of genetic variations (with a primary focus on substitutions) at time of virological/clinical flare will be tabulated in frequency outputs (n, %), based on NGS data (1% and 15% cut-off), for participants with viral sequence information available at time of flare.

The return to wild type for subjects with virologic/clinical flare and genetic variations at time of virologic/clinical flare will be tabulated in frequency outputs based on NGS data, as well as the genetic variations in subjects who did not return to wild type.

- Time of Re-treatment during Post-treatment Follow-up

For virologically suppressed participants who meet NA re-treatment criteria but who don't have baseline sequence information available, the frequency of genetic variations (with a primary focus on substitutions) at time of meeting NA re-treatment criteria will be tabulated in frequency outputs (n, %), based on NGS data (1% and 15% cut-off), for participants with viral sequencing information available at time of meeting NA re-treatment criteria.

The return to wild type for subjects who meet re-treatment criteria during follow-up and genetic variations at time of meeting the re-treatment criteria will be tabulated in frequency outputs based on NGS data, as well as the genetic variations in subjects who did not return to wild type.

- Other Post-Baseline

The frequency of variant of genetic variations at other time points will be tabulated in frequency outputs (n, %), based on NGS data (1% and 15% cut-off), and the genetic variations will be listed for all subjects. Time points of specific interest are end-of-treatment, time point of re-treatment, and end-of-study.

7.5.2. Over the Study Period

For all subjects, listings with relevant baseline disease and demographic characteristics, session info, all genetic variations at baseline (if available), at time of virologic breakthrough (if applicable), at end of study treatment, and at end of study will be generated.

For all subjects, listings with relevant baseline disease and demographic characteristics, session info, and aggregate post-baseline sequence data over the whole treatment period, and aggregate post-baseline sequence data over the whole study period will be generated.

7.6. HBV genotype

For all subjects for whom viral sequencing is performed, also an HBV genotype will be reported using the HBV full genome sequence and phylogenetic analysis. The number and percentage of subjects by HBV genotype for study analysis will be tabulated.

8. PHARMACOKINETICS/PHARMACODYNAMICS

8.1. Pharmacokinetics

Two types of PK analyses will be conducted, including noncompartmental analysis in the PK sub-study participants and population PK analysis in all participants. Details of the PK analyses will be described in a separate analysis plan and results will be reported separately.

8.2. Pharmacokinetic/Pharmacodynamic Relationships

Relationships of PK parameters for JNJ-3989, JNJ-6379, JNJ-3924 and/or NAs (ETV, TAF and/or TDF), as applicable, with selected efficacy and with selected safety endpoints will be evaluated, applying graphical tools and, if feasible, statistical models.

Modeling of key pharmacodynamic parameters (e.g. HBsAg, HBV DNA) may be performed using population pharmacokinetics/pharmacodynamics (PK/PD). Details of the PK/PD analyses will be described in a population PK/PD analysis plan and results will be presented in a separate report.

8.3. Immune Response

Descriptive statistics (for example, may include n, mean, SD, CV, geometric mean, median, minimum, and maximum) will be used to describe the magnitude of the IFN- γ T cell response or the CD4+ and CD8+ T-cell responses (expressing at least 1 cytokine such as IL-2, TNF- α or IFN- γ specific to any HBV antigen) as defined by ELISpot and/or ICS, respectively. Changes from baseline (if present) will also be tabulated for PBMCs during study intervention and follow-up. The proportion (%) of CHB participants with positive responses based on the magnitude of the IFN- γ T cell response or the CD4+ or CD8+ T cells expressing at least 1 of the cytokines amongst IL-2, TNF- α or IFN- γ for 1 of the HBV antigens as defined by ELISpot and/or ICS, respectively, will be determined.

Graphs showing the individual subject values as dots, together with horizontal lines indicating the corresponding median and interquartile range (IQR) per time point for each assay will be presented. The spaghetti plots will be used to show the patient profiles per time point for each assay. A graph showing the median and IQR over time by intervention arm will be presented. A bar chart will be used to show the breadth of response (i.e. HBV-specific immune response rate for combinations of peptide pools).

For intracellular cytokine staining (ICS), for all cytokine combinations (IFN γ and/or TNF α and/or IL-2), pie charts will be presented to reflect the distribution of each of the cytokine combinations (i.e. the proportion of a specific cytokine combination of the CD4 or CD8 T-cells secreting at least one cytokine), and bar charts will be presented to reflect the mean magnitude of each combination.

9. PATIENT-REPORTED OUTCOMES

The impact of HBV treatment on participants will be assessed using PROs at predefined time points. The following PRO instruments will be used: HBV-specific self-stigma scale and EQ-5D-5L questionnaire. All PRO analyses will be performed using the ITT analysis set.

